8.3.6 SERIOUS ADVERSE EVENT REPORTING

The study clinician will immediately report to the sponsor any serious adverse event, whether or not considered study intervention related, including those listed in the protocol or package insert and must include an assessment of whether there is a reasonable possibility that the study intervention caused the event. Study endpoints that are serious adverse events (e.g., all-cause mortality) must be reported in accordance with the protocol unless there is evidence suggesting a causal relationship between the study intervention and the event (e.g., death from anaphylaxis). In that case, the investigator must immediately report the event to the sponsor.

All serious adverse events (SAEs) will be followed until satisfactory resolution or until the site investigator deems the event to be chronic or the participant is stable.

The study sponsor will be responsible for notifying the Food and Drug Administration (FDA) of any unexpected fatal or life-threatening suspected adverse reaction as soon as possible, but in no case later than 7 calendar days after the sponsor's initial receipt of the information. In addition, the sponsor must notify FDA and all participating investigators in an Investigational New Drug (IND) safety report of potential serious risks, from clinical trials or any other source, as soon as possible, but in no case later than 15 calendar days after the sponsor determines that the information qualifies for reporting.

8.3.7 REPORTING EVENTS TO PARTICIPANTS

Participants will be notified of any abnormal clinical lab findings and directed to appropriate medical care. In the event that a participant's pregnancy test returns positive, the participant will be notified immediately and exited from the study.

8.3.8 EVENTS OF SPECIAL INTEREST

Not applicable.

8.3.9 REPORTING OF PREGNANCY

Subjects will be asked to immediately inform the study team and their doctor if any of the following occur:

- They become pregnant while taking the study drug
- They miss their menstrual period, or experiences unusual menstrual bleeding
- They stop using birth control
- They think, FOR ANY REASON, that they may be pregnant

Pregnancies occurring while the subject is participating in the study or within 30 days after the subject's administration of study drug are considered expedited reportable events. The pregnancy will be considered an immediately reportable event and will be reported to the study PI within 5 business days of the site PI becoming aware of the event.

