2.3.1. B Risks of ixekizumab

The risks of ixekizumab are summarized below from the package insert provided by Ely Lilly (available at: <https://uspl.lilly.com/taltz/taltz.html#pi>) and are based on bi-weekly treatment in three placebo-controlled studies for adult patients with plaque psoriasis (n = 1167). Similar side effect profiles were observed in other studies that dosed ixekizumab once a month.

Most common ($\geq 1\%$) adverse reactions associated with ixekizumab treatment are injection site reactions, upper respiratory tract infections, nausea, and tinea infections. Adverse reactions that occurred at rates less than 1% in the ixekizumab group and more frequently than in the placebo group during the 12-week induction period included rhinitis, oral candidiasis, urticaria, influenza, conjunctivitis, inflammatory bowel disease, angioedema, and abnormal laboratory values (complete blood count). Treatment with ixekizumab may worsen symptoms of active tuberculosis (TB) infection. Patients will be evaluated for TB infection prior to initiating treatment with ixekizumab.

In the pooled data, infections occurred in 27% of subjects treated with ixekizumab compared to 23% of subjects treated with placebo. Serious infections occurred in 0.4% of subjects treated with ixekizumab and in 0.4% of subjects treated with placebo.

There are no available data on ixekizumab use in pregnant women to inform any drug associated risks. Human IgG is known to cross the placental barrier; therefore, ixekizumab may be transmitted from the mother to the developing fetus. There are no data on the presence of ixekizumab in human milk, the effects on the breastfed infant, or the effects on milk production.

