5 STUDY POPULATION

5.1 INCLUSION CRITERIA

1. Written informed consent (and assent when applicable) obtained from subject;
2. Ability for subject to comply with the requirements of the study as determined by the PI;
3. Men and women, age 18-70 years;
4. Participants must meet DSM-5 criteria for Major Depressive Disorder [MDD]) in a current major depressive episode (MDE) as determined by a study psychiatrist and confirmed using the Structured Clinical Interview for DSM-5 Research Version (SCID-5-RV);
5. Participants have had ≥ 2 adequate trials of antidepressants/augmentation strategies during current episode. (Refer to ATRQ Guidelines for Completion for guidelines on dose/duration required for a trial to be considered adequate.);
6. If patient is on antidepressant medication, they must be on a stable dose for >4 weeks prior to treatment;
7. Quick Inventory of Depressive Symptoms – Clinician Administered (QIDS-C) score ≥ 14
8. If female of childbearing potential, must agree to use of a medically accepted form of contraception, or else agree to abstinence until 6 months after the last dose of study drug.
9. Male patients, if heterosexually active with a partner who is female of childbearing potential, pregnant, or breastfeeding, must agree to barrier contraception for the treatment period and for at least 6 months after the last dose of study drug. Female partners of male participants must use at least one form of highly effective contraception starting at least one cycle prior to male patient study drug initiation until 6 months after the last dose of study drug.

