5.2 EXCLUSION CRITERIA

1. A primary psychiatric diagnosis other than MDD as defined by DSM-5; [comorbid anxiety disorders (including agoraphobia, generalized anxiety disorder, social anxiety disorder and panic disorder) and posttraumatic stress disorder (PTSD) are allowed];
2. Has a history of schizophrenia or other psychotic disorder, major depressive disorder with psychotic features, or bipolar I or II disorder;
3. Diagnosis of a major neurocognitive disorder;
4. Meets criteria for a moderate or severe substance use disorder within the past 6 months, with the exception of nicotine use disorder;
5. The patient is pregnant or breastfeeding;
6. Any contraindication to MRI or gadolinium including claustrophobia, any trauma or surgery which may have left magnetic material in the body, magnetic implants or pacemakers, inability to lie still for 1 hour or more, any known allergy to gadolinium;*
7. Positive urine toxicology screen for illicit drugs at the time of screening;
8. Serious and imminent risk of self-harm or violence as determined by the PI;
9. History of suicide attempt in the past 2 years or screening CSSRS Ideation Score >2 in the past month;
10. Clinically significant abnormalities of laboratory tests or physical examination;
11. Any unstable medical illnesses including hepatic, renal, gastroenterological, respiratory, cardiovascular (including ischemic heart disease); endocrinologic, neurologic (including history of severe head injury), immunologic, or hematologic disease;
12. Presence of TB as assessed by Quantiferon Gold test at screening;
13. Concomitant treatments with other biologics or other immune-suppressant agents; PRN use of NSAIDs is permissible;
14. Female participants who are pregnant, breastfeeding, or may become pregnant, or unwilling to practice birth control during participation in the study or the 6 months following;
15. Presence of a condition or abnormality that in the opinion of the Investigator would compromise the safety of the patient or the quality of the data.

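### Expedited pregnancy reporting stops 30 days after study drug and does not mention partners, while contraception is required until 6 months after the last dose

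*Combined protocol and SAP*

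**What the plan says.** **Contraception.** Section 5.1, criterion 8, asks female participants of childbearing potential to use contraception "or else agree to abstinence until 6 months after the last dose of study drug". Under criterion 9, male participants with a relevant partner "must agree to barrier contraception for the treatment period and for at least 6 months after the last dose of study drug". The same criterion extends to the partner: "Female partners of male participants must use at least one form of highly effective contraception", again until 6 months after the last dose. Section 5.2, criterion 14, uses a different starting point and excludes women who are "unwilling to practice birth control during participation in the study or the 6 months following".

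**Pregnancy reporting.** Section 8.3.9 gives expedited-reportable status to "Pregnancies occurring while the subject is participating in the study or within 30 days after" administration of study drug. Its first request to participants is limited in time: they should tell the team if "They become pregnant while taking the study drug". The other three requests (missed period or unusual bleeding, stopping birth control, any suspicion of pregnancy) have no end date. Partners are not mentioned.

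**Reason for care.** Section 2.3.1.B states: "There are no available data on ixekizumab use in pregnant women to inform any drug associated risks". It adds that the antibody may reach the fetus.

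**Neighbouring rules.** The last scheduled pregnancy test is at week 6 (Sections 1.3 and 8.1). A positive test leads to exit from the study (Section 8.3.7). A congenital anomaly in the offspring of an exposed subject is an SAE (Section 8.3.2). SAE collection ends 30 days after the last day of participation in Section 8.3.4, but 30 days after the last dose in Section 8.3.5.

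**The concern.** The protocol imposes a 6-month precaution on three groups of people, but the matching duty to report a pregnancy lasts about one month and is written around the participant alone. A pregnancy beginning in months 2 to 6 after the last dose, or in a partner, falls outside any rule that obliges the site to report it expeditiously or to follow it. The protocol itself says no data in pregnant women are available, so even one such pregnancy would be informative.

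A second gap lies behind the first. The protocol classes a birth defect as an SAE, yet both SAE windows close within weeks of exit, and no section describes following a pregnancy to its outcome.

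**Working it through.** The plan gives no figure for this point, so there is none to reproduce. The check is calendar arithmetic.

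**Inputs**
- Last dose: week 4, day 28. Exit: week 8, day 56 (Section 1.1, Participant Duration).
- Pregnancy reporting: during participation, or 30 days after administration (Section 8.3.9). Administration is read as the last dose, the reading that favours the protocol.
- Contraception: 6 months after the last dose (Section 5.1), taken as 183 days. This is an assumption; 180 to 184 days is the plausible range. In criterion 8 the 6 months is read as applying to contraception as well as to abstinence.
- Visit windows: 3 days in Section 1.3, 5 days in Section 8.2.

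**End dates, nominal schedule**
- Pregnancy reporting: the later of day 56 and day 28 + 30 = day 58, so day 58.
- Contraception, criteria 8 and 9: 28 + 183 = day 211.
- Contraception, criterion 14, counted from exit: 56 + 183 = day 239, which is 28 days later.
- SAE collection: 28 + 30 = day 58 (Section 8.3.5) or 56 + 30 = day 86 (Section 8.3.4).

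**Share of the post-dose contraception period with a reporting duty**

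Share = days from last dose to end of reporting ÷ days from last dose to end of contraception.
- Nominal: 30/183 = 16%, leaving 153 days. With 180 or 184 days: 30/180 = 17%, 30/184 = 16%.
- Week 4 visit early and exit late, 3-day window: exit falls 28 + 3 + 3 = 34 days after the last dose, and 34/183 = 19%.
- The same with the 5-day window: 28 + 5 + 5 = 38 days, and 38/183 = 21%.
- Against criterion 14: 30/(28 + 183) = 30/211 = 14%.
- Lending pregnancy reporting the longer SAE window of Section 8.3.4: 86 − 28 = 58 days, and 58/183 = 32%. With the 5-day visit windows added: 68/183 = 37%.

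**Counted from the first dose**
- Nominal: 58/211 = 27%.
- With the longer SAE window: 86/211 = 41%.

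The duty covers less than half of the period on every reading.

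**Birth defects.** SAE collection closes by day 58 or day 86. Birth follows conception by months, so a pregnancy conceived on study and carried to term would deliver after both dates, even if it began inside the present 30-day window. Lengthening the pregnancy window alone does not cure this.

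**The case against.** A reader might infer that late pregnancies are unmonitored, that partner pregnancies are never reportable, or that a birth defect could not come to light. The documents do not go that far.

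- Three of the four notification requests are open-ended, so a participant who conceives in month 4 has been asked to tell the team. What is missing is a stated duty on the site once told.
- Section 8.3.9 gives expedited status to pregnancies inside the window. It does not say that later ones are to be ignored.
- The absence of partners is silence, not exclusion. The reporting sentence is not expressly limited to the participant's own pregnancy.
- Section 5.1 gives no reason for its 6 months and does not call them an exposure period. Section 2.3.1.B mentions transfer to the fetus but no duration. A contraception period can carry a safety margin, so different lengths are not in themselves contradictory.
- Consent pages were removed from the public documents and may contain instructions on late or partner pregnancies.
- With up to 20 participants of both sexes aged 18 to 70, few such events are likely. Section 3 counts adverse events only to study exit, so a late pregnancy would not enter the primary results.

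All of this stands and limits the wording. It does not supply the missing duty: no section requires a pregnancy after day 58 to be reported expeditiously, tests for it or follows it, and no section names partners although criterion 9 places a requirement on them. The difference between criteria 8 and 14 is minor, since anyone who meets the later date meets both.

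**Conclusion.** The point holds in a limited form. The stated pregnancy reporting duty covers about 16% of the 6 months after the last dose for which contraception is required, and about 32% on the nominal schedule if the longer SAE window is applied. Partners are not addressed. Later voluntary reports are possible, but no reporting duty, scheduled test or outcome follow-up is stated for them. This rests on taking 6 months as about 183 days, on reading administration as the last dose, and on the public text without its consent pages.

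It is a worthwhile, inexpensive improvement to participant and fetal safety, not a flaw in the analysis. Treatment completion, its confidence interval and the sample size are unchanged. Nothing here says how long contraception should last.

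**What to change.** - Reconcile Sections 5.1, 5.2 and 8.3.9 so that pregnancy reporting ends on the same date as whatever contraception period the sponsor keeps. With the present 6 months after the last dose, the window would grow from about 30 to about 183 days.
- Name pregnancies in partners of male participants explicitly in Section 8.3.9.
- Count criteria 8, 9 and 14 from one event.
- At the exit visit, instruct participants to report a pregnancy up to that date, and check that the consent form agrees.
- State that a reported pregnancy is followed to outcome. Reconcile the SAE windows in Sections 8.3.4 and 8.3.5 so that a congenital anomaly after an exposed pregnancy is captured whenever SAE collection otherwise closes.

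**Cost.** Protocol wording, consent wording if needed, and an instruction at exit. The site must accept and follow a rare late report after a participant has left. No visit is added, and sample size and analysis do not change.

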8.4 UNANTICIPATED PROBLEMS

8.4.1 DEFINITION OF UNANTICIPATED PROBLEMS (UP)

The Office for Human Research Protections (OHRP) considers unanticipated problems involving risks to participants or others to include, in general, any incident, experience, or outcome that meets all of the following criteria:

- Unexpected in terms of nature, severity, or frequency given (a) the research procedures that are described in the protocol-related documents, such as the Institutional Review Board (IRB)-approved research protocol and informed consent document; and (b) the characteristics of the participant population being studied;
- Related or possibly related to participation in the research (“possibly related” means there is a reasonable possibility that the incident, experience, or outcome may have been caused by the procedures involved in the research); and
- Suggests that the research places participants or others at a greater risk of harm (including physical, psychological, economic, or social harm) than was previously known or recognized.

8.4.2 UNANTICIPATED PROBLEM REPORTING

The investigator will report unanticipated problems (UPs) to the reviewing Institutional Review Board (IRB) and to the Data Coordinating Center (DCC)/lead principal investigator (PI). The UP report will include the following information:

- Protocol identifying information: protocol title and number, PI’s name, and the IRB project number;
- A detailed description of the event, incident, experience, or outcome;
- An explanation of the basis for determining that the event, incident, experience, or outcome represents an UP;
- A description of any changes to the protocol or other corrective actions that have been taken or are proposed in response to the UP.

8.4.3 REPORTING UNANTICIPATED PROBLEMS TO PARTICIPANTS

Not applicable.

9 STATISTICAL CONSIDERATIONS

9.1 STATISTICAL HYPOTHESES

- Primary Efficacy Endpoint(s):

The primary efficacy endpoint is the completion of treatment measured as the receipt of all three Ixekizumab (160 mg at week 0, 80 mg at weeks 2 and 4) to assess the safety and feasibility of ixekizumab in patients with TRD. The analysis of the primary endpoint for this study will be descriptive and no formal hypothesis testing will be conducted.

- Secondary Efficacy Endpoint(s):

Secondary efficacy endpoints include 1) Baseline-to-week-6 changes in depression severity, as measured by MADRS; 2) Response and remission rates at week 6; 3) changes in other clinical symptoms ;4)

Baseline-to-week-6 changes in RSFC as evaluated by fMRI scans and changes in BBB permeability; 5) Baseline-to-week-6 changes in blood-based immune markers, including CRP and other immune markers; 6) the relationship between baseline-to-week-6 changes in blood-based immune markers and RSFC with changes in depression severity scores. Analyses of secondary efficacy endpoints will be considered exploratory and hypothesis-generating. Therefore, no formal hypothesis testing will be conducted.

9.2 SAMPLE SIZE DETERMINATION

In this study, up to 20 patients will be enrolled. We anticipate 80% of more of the sample will complete treatment (<20% early drop out) and the treatment will be well-tolerated with no treatment-related adverse effects. A sample size of 20 patients will produce a two-sided 95% confidence interval around the proportion who completed treatment with a width equal to 0.35 when the sample proportion is 0.8. Precision was estimated using PASS 2019 (26).

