9.4 STATISTICAL ANALYSES

9.4.1 GENERAL APPROACH

Continuous variables will be summarized using the following descriptive statistics: number of non-missing values, means, standard deviations, medians, interquartile range, maximum, and minimum. Categorical variables will be summarized using number of non-missing values, counts and percentages.

Rates of events will be calculated as the ratio of the total number of events recorded divided by the total patient-time. Total patient-time will be calculated by summing the time (in study time units, e.g., days or months) that patients were at risk for a specific event from the reference time point until either study exit or the end of the time period of interest. Rates and their 95% confidence intervals will be reported.

Time-to-event variables will be summarized using the Kaplan-Meier method.

For any variable measured at multiple points in time, change from baseline will be calculated as the difference between the value of the variable at a specific point in time (e.g. 6 weeks) minus the baseline value. Relative change from baseline will be calculated as the value of a parameter at a specific point in

time minus the baseline value of the parameter divided by the baseline value of the parameter. Percent change will be calculated as the relative change multiplied by 100.

All hypothesis testing will be conducted at the 0.05 two-sided significance level unless otherwise specified. P-values will be rounded to three decimal places. P-values less than 0.001 will be reported as <0.001 in tables. P-values greater than 0.999 will be reported as >0.999.

Should any of the statistical methods proposed prove unsuitable during data analysis, more appropriate methods will be used. These include data transformation (for example to a logarithmic scale) to satisfy model assumptions such as normally distributed residuals with constant variance, the application of non-parametric techniques or the use of a different link function or modeling technique. The SAP will be updated with the methods used and the justification for the change prior to data set and database lock.

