9.4.2 ANALYSIS OF THE PRIMARY EFFICACY ENDPOINT(S)

The primary efficacy endpoint is the completion of treatment measured by the receipt of all three ixekizumab injections (160 mg at week 0, 80 mg at weeks 2 and 4) to assess the safety and feasibility of ixekizumab in patients with TRD. The analysis of the primary endpoint for this study will be descriptive. The proportion of enrolled patients that complete treatment and the corresponding 95% confidence interval will be reported.

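### Does the primary completion analysis need a named 95% confidence interval method?

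*Combined protocol and SAP*

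**What the plan says.** Section 9.2 sets the maximum size ("In this study, up to 20 patients will be enrolled") and the expectation: "We anticipate 80% of more of the sample will complete treatment (<20% early drop out". It then gives its only precision figure, a two-sided 95% "confidence interval around the proportion who completed treatment with a width equal to 0.35 when the sample proportion is 0.8". The source cited is software, not a formula: "Precision was estimated using PASS 2019 (26".

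Section 9.4.2 gives the primary analysis in one line: "The proportion of enrolled patients that complete treatment and the corresponding 95% confidence interval will be reported". No interval type is named.

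Section 9.4.1 is equally general. For categorical data it says "Categorical variables will be summarized using number of non-missing values, counts and percentages", and it mentions confidence intervals only for event rates per patient-time. It also carries a reserve clause: "Should any of the statistical methods proposed prove unsuitable during data analysis, more appropriate methods will be used". Such a change and its justification are to be written into the SAP before database lock.

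Section 9.1 sets the status of the result: "The analysis of the primary endpoint for this study will be descriptive and no formal hypothesis testing will be conducted".

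**The concern.** Under Section 9.4.2 the completion proportion and its interval are all there is to the primary analysis, and the interval width is the only quantitative support for n=20. The interval is nevertheless unnamed in both places.

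The stated 0.35 is not the width of the exact or the Wilson interval at 16/20, and Wald matches it closely. If Wald were carried into Section 9.4.2, it would be used where it is weakest. The plan expects 80% or more to complete, which means 16 to 20 of 20. Read strictly, the drop-out figure of under 20% means 17 to 20. A Wald interval there passes 1 or collapses to a point, and its true coverage falls well below 95%. If the exact interval were used instead, Section 9.2 would slightly overstate the precision of the design.

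**Working it through.** **Inputs.** n = 20, sample proportion 0.8 (16 completers), two-sided 95% and width 0.35, all from Section 9.2. z = 1.95996.

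**Step 1: reproduce the plan's figure.** Wald width = 2z√(p(1−p)/n) = 2 × 1.95996 × √(0.8 × 0.2/20) = 2 × 1.95996 × 0.08944 = 0.3506. This rounds to 0.35, so there is no error in Section 9.2.

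**Step 2: does 0.35 identify the method?** Other intervals at 16/20:

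- Logit: ln(0.8/0.2) ± z√(1/(20 × 0.8 × 0.2)) = 1.3863 ± 1.0957, back-transformed to 0.572–0.923; width 0.3507.
- Mid-P: 0.585–0.933; width 0.3479.
- Agresti–Coull: ñ = 20 + z² = 23.841 and p̃ = (16 + z²/2)/ñ = 0.7517, giving 0.578–0.925; width 0.3469.
- Wilson: width = 2z√(p(1−p)/n + z²/4n²)/(1 + z²/n) = 2 × 1.95996 × √(0.008 + 0.002401)/1.19207 = 0.3354 (0.584–0.919).
- Clopper–Pearson (exact): 2.5th percentile of Beta(16, 5) to 97.5th percentile of Beta(17, 4) = 0.563–0.943; width 0.3793.

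Four methods round to 0.35. Wald and logit differ by only 0.0001, so a two-decimal width cannot separate them. Exact and Wilson are ruled out as the source of the planning figure, but that does not rule them out for the analysis.

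**Step 3: what the choice does over the expected results.**

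| Completers | Wald | Wilson | Exact |
|---|---|---|---|
| 16/20 | 0.625–0.975 | 0.584–0.919 | 0.563–0.943 |
| 17/20 | 0.694–1.006 | 0.640–0.948 | 0.621–0.968 |
| 18/20 | 0.769–1.031 | 0.699–0.972 | 0.683–0.988 |
| 19/20 | 0.854–1.046 | 0.764–0.991 | 0.751–0.999 |
| 20/20 | 1–1 | 0.839–1 | 0.832–1 |

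The Wald faults show on the face of the output. The largest gap between the Wilson and exact limits is at the upper limit for 16/20: 0.9427 − 0.9193 = 0.0234. One participant is 1/20 = 0.05.

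**Step 4: coverage.** For each true completion rate, binomial probabilities were summed over the counts whose interval contains that rate (n = 20).

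| True rate | Wald | Wilson | Exact |
|---|---|---|---|
| 0.80 | 92% | 96% | 98% |
| 0.85 | 82% | 98% | 98% |
| 0.90 | 88% | 96% | 99% |
| 0.95 | 64% | 92% | 98% |

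The Wald column is poor, but it applies only if Wald is used for the analysis. Wilson is not perfect either: just above a true rate of 0.991 its coverage drops to about 84%, because only 20/20 then gives an interval containing the true rate. The exact interval stays above 95% throughout.

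**Step 5: what holds whatever the method.** Exact: 0.379 − 0.35 = 0.029 wider than stated. Wilson: 0.35 − 0.335 = 0.015 narrower.

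**The case for a change.** The strongest reply is that a primary analysis should not leave its only inferential element open. The reserve clause in Section 9.4.1 covers methods that were proposed, and here none was. The study is open-label, so the interval could be chosen once the count of completers is known. A result of 17 or more, where Wald leaves the 0–1 range or collapses, is also likely: its probability is 41%, 65%, 87% and 98% at true completion 0.80, 0.85, 0.90 and 0.95. Naming the method would cost about two sentences.

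Most of this is true. The method is unnamed, the clause does not strictly reach it, and writing it down would be cheap. What does not stand is the step from a planning width to a Wald analysis: no section says so, and the width fits intervals that behave better. Nor is there much to gain from a late choice. No threshold or test depends on a limit, the choice between exact and Wilson moves a limit by less than 0.024, and anyone with the count can compute a preferred interval. A Wald interval of 1.00 to 1.00, or one running past 1, would be noticed and replaced.

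**Conclusion.** No change is required. The omission is real, but it is a detail that an analyst fills sensibly. The stated 0.35 is reproducible, and the exact or Wilson width differs from it by at most 0.029 at 16/20. That is too little to alter the case for a descriptive study of up to 20 patients. The serious consequences (limits above 1, zero width at 20/20, coverage of 64% to 92% at the four true rates examined) are all conditional on Wald being used in Section 9.4.2, which the documents do not state.

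This rests on three assumptions: the analyst uses an interval suited to a small binomial sample near the boundary; the completion count is reported with the percentage, as Section 9.4.1 provides; and the interval remains descriptive, as Section 9.1 says. If a success threshold for completion were ever attached to a confidence limit, the method would have to be fixed beforehand.
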